#### **3.1 Study Population**

The study will aim to recruit 42 eligible patients requiring periodontal treatment within a recruitment period of 18-24 Months.

#### **3.2 Inclusion criteria**

- Written informed consent
- Male or female 18 years to 70 years inclusive
- Periodontal treatment required at Glasgow Dental Hospital or General Dental Practice
- Patients able to travel and attend all study visits.
- Probing pocket depths >5mm on 2 or more teeth at non-adjacent sites with cumulative probing pocket depths of greater than or equal to 40mm (Cumulative probing depth is calculated by evaluating all sites on each tooth. The deepest site on each tooth is recorded and if this value is greater than 4mm this is 'counted' and the sum of all the teeth assessed in this way calculated.)

#### **3.3 Exclusion criteria**

- Known or suspected high risk for tuberculosis, hepatitis B or HIV infections
- Require interpreter/non English language written material to understand and provide, or any other reason for being unable to provide written, informed consent
- History of bleeding diathesis
- Pregnant or lactating females.
- Reported diagnosis of any systemic illnesses including cardiovascular, renal, and liver diseases, and/or regular use of medication to control systemic illness.
- Any pharmacological treatment within 1 month before the beginning of the study, including routine use of any over the counter medications.
- Specialist Periodontal treatment in the previous 6 months.

Randomisation: patients will be stratified according to smoking status then randomized to one of two groups (hand vs ultrasonic) according to the randomization schedule (permuted blocks of size 4 and 6). The randomization schedule will be computer generated and allocation will be concealed up until the point of treatment. Masking: it will not be possible to mask the clinicians providing the treatment; however the researcher collecting the samples and undertaking the analysis will be masked to group allocation, through the use of anonymised coded samples. All other study personnel will not have access to identifiable data.

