### 1. INTRODUCTION

#### 1.1 Background

Effective root surface debridement (RSD) is essential for successful periodontal treatment. Myriad studies demonstrate that RSD may be carried out using hand or ultrasonic instruments with equal efficacy (1). Locally, effective debridement results in reduced inflammation in the gingival tissues, ultimately preserving the dentition. Systemically, RSD results in an immediate inflammatory response with elevated C-reactive protein (CRP), and cytokines (e.g. interleukin-6 and Tumor Necrosis Factor) detectable in the serum (2). This systemic inflammation may relate to systemic dissemination of bacteria from the periodontal pockets into the circulation, during instrumentation. Bacteria are detectable in serum immediately after instrumentation (3). The incidence of the bacteraemia varies considerably between different studies,

ranging from 13% of patients (4) to 43% (5) to 55% (6). These studies used different methods of instrumentation; Kinane et al used full mouth ultrasonic scale, Zhang et al used a mixture of hand and ultrasonic instruments, and Heimdahl et al used curettes only. Whilst tempting to speculate that ultrasonic instrumentation induces less bacteraemia than hand instrumentation, *there is no direct comparison of the effect of ultrasonic instrumentation with hand instrumentation on post treatment systemic inflammation.*

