## **4 Trial procedures**

### **4.1 Study schedule**

Patients will attend Glasgow Dental Hospital for screening, baseline, treatment, then Day 1 after treatment, Day 7 after treatment, and review (day 90 after treatment). Screening visits may be undertaken by GDP. The visits are labelled as per the flow chart/table with the purpose of the visit.

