## 4.2 Study Outcome Measures

### 4.2.1 Primary Outcome Measure

*Changes in serum CRP pre compared with post treatment.*

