#### **Primary Outcome:**

Changes in serum CRP. This will be measured:

- Pre-intervention, at baseline visit (as per flowchart)
- Day 1, day 7 and day 90 post-intervention

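### The washout for earlier periodontal treatment depends on who gave it, so debridement in general practice shortly before the baseline blood is not excluded and may disturb the baseline CRP

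*Combined protocol and SAP*

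**What the plan says.** Section 3.3 and the synopsis exclude patients with "Specialist Periodontal treatment in the previous 6 months". Neither defines Specialist, and neither mentions treatment by a general dentist or hygienist.

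The trial is open to patients from that setting. Section 3.2 admits patients with "Periodontal treatment required at Glasgow Dental Hospital or General Dental Practice". Section 3.4 lists general dentists and dental care professionals among the staff who may approach a patient, and section 4.1 adds: "Screening visits may be undertaken by GDP".

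Section 1.1 gives the biological premise: "RSD results in an immediate inflammatory response with elevated C-reactive protein (CRP". It does not tie this to the type of operator and does not say how long the rise lasts.

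The primary outcome in section 4.2.1 is "Changes in serum CRP pre compared with post treatment". The SAP takes one pre-intervention CRP, at the baseline visit, and repeats it at Days 1, 7 and 90.

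The only other exclusion for recent treatment in section 3.3 concerns medicines: "Any pharmacological treatment within 1 month before the beginning of the study, including routine use of any over the counter medications".

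**The concern.** The criterion sorts patients by provider, while the protocol's own premise concerns the procedure. On a literal reading, a patient debrided by a specialist five months before entry is excluded, and a patient who had the same procedure in general practice the day before the baseline blood is not. Patients are referred in or come through general practice, so earlier scaling there is foreseeable.

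If the baseline blood falls within the response to that earlier procedure, the reference value for the primary outcome is off for a reason unrelated to the allocated instrument. Baseline serum cytokines, GCF cytokines and plaque microbiome are exposed in the same way. With a planned 17 evaluable patients per arm, a few such patients add noise to the primary comparison and may fall unevenly between arms by chance.

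**Working it through.** **1. Is the gap closed elsewhere?**
- Section 3.2: the pocket-depth threshold can still be met after recent scaling, so it does not screen these patients out.
- Section 3.3, medicines: read literally, this could catch debridement done under local anaesthetic or followed by analgesics. It does not say so, and it would miss drug-free scaling. Coverage is incidental at best. The synopsis gives 3 months for this window and section 3.3 gives 1 month; the two need reconciling in any case.
- Randomisation: smoking is the only stratification factor.
- SAP, general principles: covariate adjustment is optional, and the list names neither baseline CRP nor recent dental treatment.

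The gap is therefore open in the text.

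**2. The plan's own sample size.** Inputs from the sample size section: difference 3 mg/l, SD 3 mg/l, 5% significance (two-sided assumed, as sidedness is not stated), 80% power. The two-sample t-test solution is 16.71, so 17 per arm and 34 in total, as stated. Power at 17 per arm is 0.807. Dropout: 34/(1 - 0.20) = 42.5, against the 42 planned. There is almost no reserve above 80%.

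**3. Illustration of the loss.** Two inputs are not in the documents and are assumed: the share f of patients with a disturbed baseline, and the shift s in their baseline CRP. The top value of s, 3.5 mg/l, borrows the size of the difference between debridement schedules quoted in the sample size section. It is not an estimate of residual CRP elevation after scaling in practice. The shift is taken as independent of arm and the change score as unadjusted for baseline CRP:

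SD = sqrt(3² + f(1 - f)s²)

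Example, f = 0.30 and s = 3.5: f(1 - f)s² = 0.21 × 12.25 = 2.57; SD = sqrt(11.57) = 3.40; standardised difference 3/3.40 = 0.88; t-test power at 17 per arm = 0.70.

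| Share f | Shift s (mg/l) | SD (mg/l) | Power at 17 per arm | Per arm for 80% |
|---|---|---|---|---|
| none | none | 3.00 | 0.81 | 17 |
| 5% | 2 | 3.03 | 0.80 | 18 |
| 5% | 3.5 | 3.10 | 0.78 | 18 |
| 10% | 2 | 3.06 | 0.79 | 18 |
| 10% | 3.5 | 3.18 | 0.76 | 19 |
| 30% | 2 | 3.14 | 0.77 | 19 |
| 30% | 3.5 | 3.40 | 0.70 | 22 |

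**4. Chance imbalance.** The standard error that the disturbed baselines alone add to the difference between arms is s × sqrt(2f(1 - f)/17). At f = 10%, s = 3.5 this is 0.36 mg/l; at f = 30%, s = 3.5 it is 0.55 mg/l, against a target difference of 3 mg/l. This is the same added variance as in step 3, expressed on the scale of the treatment effect, and not a further loss.

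**The case against.** The strongest reply is that the effect may be small. The described route is referral, new-patient clinic, treatment plan and then a separately booked baseline visit, so few patients may have been debrided just before the blood is taken. At a 5% share, power stays at 0.78-0.80. Adjusting for baseline CRP in the planned models would recover part of the loss. Both points stand. They limit the size of the problem but do not close the gap, because the plan does not commit to that adjustment and would not know who was affected.

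Four stronger readings are tempting, and the documents do not support them.
- A reader might infer that such a patient's baseline CRP has definitely moved. Section 1.1 calls the rise immediate but gives no duration. A shift is well supported only when debridement came very close to the baseline blood. At longer intervals it is an inference, although the Day 1 and Day 7 samples show that the plan looks for a response over that span.
- A reader might infer bias between hand and ultrasonic arms. Eligibility precedes allocation, so none is expected.
- A reader might infer that the measured change is always attenuated. A raised baseline understates a Day 1 rise, but it enlarges a later fall from baseline. The variance argument holds; a single direction does not.
- A reader might infer that a long washout is needed, for example one matching the 90-day follow-up. Follow-up length says nothing about CRP recovery, and deferral could delay care.

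**Conclusion.** The concern holds in limited form. The text leaves non-specialist subgingival treatment before baseline uncovered, and by the protocol's own premise this may disturb the single baseline value on which the primary outcome rests. The consequence is extra variance and chance imbalance. Under assumed shares of 5-30% and shifts of 2-3.5 mg/l, power falls from 0.81 to between 0.80 and 0.70. That range depends on both assumptions and on an unadjusted change score. If few patients are affected the loss is negligible, and the plan as written would not record how many were. The correction is worth making because it is cheap and protects the primary baseline.

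**What to change.** In the synopsis and section 3.3, define the criterion by procedure as well as by provider: besides specialist treatment, it should cover subgingival instrumentation by any provider within a short window before the baseline blood. Define Specialist. The investigators should set the window and justify it from the expected CRP recovery time; the 1-month window that section 3.3 applies to medicines is one reference point, not a derived answer.

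Record the date and type of last scaling on the CRF at screening and baseline, where medical history is already taken. The number of patients affected can then be reported.

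If patients are to be deferred, reconcile this with the screening visit text in section 4.1, which tells them that their care is the same whether or not they take part. The baseline visit itself includes initial treatment.

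Cost: one amendment line and one CRF item. Some baseline visits will be delayed or some patients not enrolled, with a small effect on accrual, and deferred patients need their eligibility checked again. The sample size does not change.

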### **3.4 Identification of participants and consent**

Patients will be identified by the CI or other clinician responsible for the patient. Patients will be screened at this time to establish eligibility. The inclusion/exclusion criteria will be evident from the information taken as part of the normal clinical procedure (eg history, examination and treatment plan). Eligible patients will be initially informed of the existence of the study and approached by the consultant or his/her representative who is treating the patient (E.g. specialist trainee/house officer/GDP/DCP). This initial contact will be to provide the patient with the Participant Information Leaflet (PIL) and establish whether they would consider taking part. At the subsequent visit, (Screening visit), the CI/CO/Registrar/consultant or research nurse will ask whether the patient would like to take part and obtain consent. At each stage, it will be made clear to the patient that that participation is voluntary and they can leave the study at any time without their care being affected.

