#### **Screening visit: New patient assessment**

Patients are referred then appointed on a new patient consultant clinic at which a clinical history and clinical examination are completed by the consultant or his/her staff. A treatment plan is then agreed with the patient. If this treatment plan includes periodontal treatment at Glasgow Dental Hospital and the patient is eligible to take part, then the patient will be provided with written and verbal information about the study. The patient will be asked to give an initial indication as to whether they would consider taking part – with emphasis that they should take time to consider the PIL and will have the opportunity to ask further questions, and that their treatment remains unaltered irrespective of their participation. If the patient indicates they would consider participation in the study, they will be appointed jointly to the GDHCRF and the hygienist / registrar (baseline visit).

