#### ***Stratification and Randomization Methods***

Our target population is that of patients suffering from periodontal disease.

Randomization to either intervention (hand instrumentation or ultrasonic instrumentation) will be performed using a computerised random number generator (using permuted blocks of size 4 and 6). Patients will be stratified according to smoking status prior to randomization.

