#### ***Sample Size***

The sample size calculation is based on data from previous published studies that measured changes in CRP following periodontal treatment. From these studies a difference of 3.5 mg/l (SD=3 mg/l) in CRP was detected between the two groups receiving different schedules of periodontal treatment (quadrant vs full mouth debridement) at primary endpoint. Therefore at 80% power and a 5% significance level, a sample size of n=34 (17 in each group) is required to detect a minimum difference of at least 1 standard deviation (3 mg/l) between the change in CRP levels from baseline to primary endpoint between the two groups (hand vs ultrasonic). To account for potential drop out of 20% we aim to recruit 42 eligible patients to the study.

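### The protocol prints its block lengths in a small open-label trial where recruiting and treating roles partly overlap; it should keep the lengths, and the sequence of past allocations, from those who enrol

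*Combined protocol and SAP*

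**What the plan says.** - **Schedule.** Section 3.3 allocates "according to the randomization schedule (permuted blocks of size 4 and 6)". Section 5.1, Stratification and Randomization Methods, repeats this as a "computerised random number generator (using permuted blocks of size 4 and 6)" and adds: "Patients will be stratified according to smoking status prior to randomization". The order and mix of the two lengths are not given.
- **Masking.** Section 3.3 says "it will not be possible to mask the clinicians providing the treatment". Laboratory and analysis staff work from coded samples.
- **Who recruits and who treats.** Section 3.4 has the CI or the responsible clinician identify patients. At the next visit "the CI/CO/Registrar/consultant or research nurse will ask whether the patient would like to take part and obtain consent". Willing patients are then handled as section 4.1 (Screening visit) describes: "they will be appointed jointly to the GDHCRF and the hygienist / registrar (baseline visit)". The Baseline visit text lets training-grade staff as well as hygienists give the initial treatment.
- **Safeguards.** Under Allocation Concealment in section 5.1, a team member who does not deliver treatment makes the allocation, and an opaque envelope is opened just before treatment begins. Under Blinding, clinicians do not know the arm until then.
- **Size and pace.** There are 42 patients over 18 to 24 months, about 1.8 to 2.3 a month, from one department.

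**The concern.** An envelope hides the current assignment. It does not hide the pattern that past assignments leave behind. Within each stratum every completed block returns the arms to balance, so whoever has followed the past allocations knows which arm is behind and therefore more likely next. Here treatment is open, patients come from one department at about two a month, and the registrar role appears both among those who take consent and among those to whom patients are then appointed. No section bars a treating clinician from recruiting.

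If someone with an expectation about the next arm delayed or declined particular patients, the arms could differ in prognosis before treatment, and the CRP comparison would carry that difference. With 42 patients even a modest difference matters. Printing the lengths in a document that recruiting staff use makes the inference somewhat sharper for no benefit.

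**Working it through.** **1. The plan's own figure.** The documents give no guess probability; their relevant figure is the sample size: "a sample size of n=34 (17 in each group) is required". A two-sample t-test with a difference of 1 SD (3 mg/l, SD 3 mg/l), two-sided 5% and 80% power needs 16.7, so 17 per group (power 80.7%). That reproduces the plan and gives 1:1 allocation. With 20% dropout, 34/(1 − 0.20) = 42.5, against 42 stated; the difference is immaterial here.

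**2. Guessing without knowing the lengths.** Guess the arm that is behind in the stratum, and toss a coin when level. For a block of 2m, the expected number of correct guesses is m + 4^m/(2·C(2m,m)) − 1/2.
- Block of 4 (m = 2): 2 + 16/12 − 0.5 = 2.833, and 2.833/4 = 70.8%.
- Block of 6 (m = 3): 3 + 64/40 − 0.5 = 4.1, and 4.1/6 = 68.3%.
- One of each: (2.833 + 4.1)/10 = 69.3%.

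In a simulation of 42 patients in two smoking strata, with incomplete last blocks, the guess is right 68.3% of the time. Assumptions: two strata, 20% to 50% smokers, lengths drawn at random with equal probability. The rule uses only the running excess, so it needs no block length.

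**3. What knowing the lengths adds.** A best guesser who knows the lengths are 4 and 6 is right 68.1% of the time for 21 patients in one stratum and 68.9% for 42. That is no better on average. The gain is certainty. For example, when one arm is three ahead, the block must be a six and the next three assignments are fixed. Certain assignments make up about 5.5% to 6.3%, depending on stratum size. With strata of 28 and 14 (assumed), the guess is right about 68.5%, at least 75% sure for about 46% of patients, and certain for 5.9%.

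**4. Incomplete knowledge.** An assignment is known only after the envelope is opened at treatment. The simple guess then falls as follows:

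| What the guesser lacks | Correct guesses |
|---|---|
| Nothing (full ordered history by stratum) | 68% |
| Latest 1 recruit untreated | 62–63% |
| Latest 2 untreated | 58–60% |
| Latest 3 untreated | 56–58% |
| Does not track strata | 63% |

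**5. What steering would do, if it happened.** Suppose enrolment follows the guess and shifts prognosis by d SD between patients expected in the two arms. The expected bias is d(2p − 1), where p is the probability of a correct guess. With p = 0.685 this is 0.5 × 0.37 = 0.185 SD, or 1 × 0.37 = 0.37 SD. At SD 3 mg/l that is about 0.6 or 1.1 mg/l. Type I error of an unadjusted t-test, by simulation with 28/14 strata:

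| Scenario | d = 0.5 | d = 1 |
|---|---|---|
| Full history, every patient steered | about 9% | about 19% |
| Full history, half of patients steered | about 6% | 8–9% |
| Two recruits untreated, every patient steered | about 6% | about 8% |
| Two untreated and half steered | about 5% | about 6% |

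**6. Longer blocks.** With lengths 6, 8 and 10 in random order and full history, the guess is right 65%, at least 75% sure for 26%, and certain for 2%. Type I error in the first scenario is about 7–8% or 13–15%. With two recruits untreated, longer blocks show no gain.

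The price is balance. Blocks of 4 and 6 leave an arm at most 3 ahead in each of two strata, so at worst 24/18, with relative efficiency 4·24·18/42² = 0.98. Blocks up to 10 allow 5 ahead in each, so at worst 26/16, with 4·26·16/42² = 0.94. Typical splits are much closer.

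**The case against.** - **The 68% is a ceiling.** It needs one person who knows all earlier allocations, in order and by stratum, with nobody awaiting treatment. The protocol describes many staff, the research nurse may take consent, and the interval between baseline visit and treatment is not stated. This stands, and is why a range is given.
- **Disclosure is not the cause.** A reader might infer that printing the lengths is what lets clinicians guess 68%. It does not: the running excess alone gives that figure. What disclosure adds is the roughly 6% of certain cases.
- **The overlap is of roles.** A reader might infer that the clinicians who treat are the same people who enrol. The text names the registrar on both sides and lets training-grade staff treat, but does not say the individuals coincide.
- **Steering is not shown.** Both treatments are described as standard and of equal efficacy, and the entry criteria are largely factual. Randomisation takes place at the baseline visit, so later removal would be a withdrawal with a recorded reason. A 1 SD shift equals the whole difference the trial is sized to detect, and the models may adjust for baseline disease, smoking and operator. So the 9% and 19% are conditional illustrations. They are not estimates for this trial.
- **Strict alternation.** A reader might assume the lengths alternate 4, 6, 4, 6, which would make more assignments certain. The wording does not exclude this, but nothing states it, and a random number generator is specified.

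The safeguards answer only part of the concern: an independent allocator and a sealed envelope prevent reading ahead but cannot prevent inference from allocations already opened.

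**Conclusion.** The point holds as a modest, cheaply corrected weakness in allocation concealment. Given complete within-stratum knowledge, up to about 68% of next assignments could be guessed, and about 56–63% if one to three recruits are untreated. Short blocks and unmasked treatment account for most of that; the printed lengths mainly add certainty for about 6%. The figures assume two smoking strata and lengths drawn at random with equal probability.

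The documents do not support a conclusion that enrolment will be steered or that the false-positive rate exceeds 5%. The reason to act is that the risk can be reduced at almost no cost.

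**What to change.** In section 3.3 and in section 5.1 (Stratification and Randomization Methods), replace the bracketed block sizes with wording such as: *permuted blocks of randomly varying length, with the lengths held in a restricted file by the list holder and not disclosed to staff who recruit or treat*.

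Add to section 3.4 or Allocation Concealment: *as far as staffing allows, those who assess eligibility and take consent do not have access to the sequence of past allocations*. This second sentence matters more, because hiding the lengths alone leaves the average guess unchanged.

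The cost is minor administration: an amendment and a restricted file. Staff who have already read the lengths cannot unlearn them, so the first change helps most if the schedule for patients not yet randomised is also regenerated. Doing so with longer lengths (for example 6, 8 and 10) is optional: it lowers the ceiling only from 68% to 65% and allows slightly more imbalance in small strata. If recruitment is complete, what remains is to report which roles enrolled and which treated.
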